## **5.4 APPROPRIATENESS OF MEASUREMENTS**

All measurements performed during this trial are standard measurements and will be performed in order to monitor subjects' safety and to determine pharmacokinetic parameters in an appropriate way. The scheduled measurements will allow monitoring of changes in vital signs, standard laboratory values, and ECG parameters that might occur as a result of administration of trial medication. The safety assessments are standard, are accepted for evaluation of safety and tolerability of an orally administered drug, and are widely used in clinical trials. The pharmacokinetic parameters and measurements outlined in Section 5.5 are generally used assessments of drug exposure.

## **5.5 DRUG CONCENTRATION MEASUREMENTS AND PHARMACOKINETICS**

Date and clock time of drug administration and pharmacokinetic sampling will be recorded in the CRFs.

### **5.5.1 Pharmacokinetic endpoints**

#### **5.5.1.1 Primary endpoints**

The following primary endpoints will be determined for BI 409306

- $AUC_{0-tz}$  (area under the concentration-time curve of the analyte in plasma over the time interval from 0 to the last quantifiable data point)
- $C_{max}$  (maximum measured concentration of the analyte in plasma)

The following primary endpoints will be determined for ethinylestradiol and levonorgestrel:

- $AUC_{0-24,ss}$  (area under the concentration-time curve of the analyte in plasma over the time interval from 0 to the last quantifiable data point)
- $C_{max, ss}$  (maximum measured concentration of the analyte in plasma)

#### **5.5.1.2 Secondary endpoints**

The following secondary endpoints will be evaluated for BI 409306:

- $AUC_{0-\infty}$  (area under the concentration-time curve of the analyte in plasma over the time interval from 0 extrapolated to infinity)

Further pharmacokinetic parameters might be calculated as appropriate.

### **5.5.2      Methods of sample collection**

#### **5.5.2.2    Plasma sampling for pharmacokinetic analysis of ethinylestradiol and levonorgestrel**

For quantification of ethinylestradiol and levonorgestrel, approximately 6 mL of blood will be taken from an antecubital or forearm vein into an EDTA (ethylenediaminetetraacetic acid)-anticoagulant blood drawing tube at the times indicated in the Flow Chart. Blood will be withdrawn by means of either an indwelling venous catheter or by venipuncture with a metal needle.

Proprietary confidential information © 2017 Boehringer Ingelheim International GmbH or one or more of its affiliated companies

The EDTA-anticoagulated blood samples will be centrifuged for about 15 min at about 2100 g and at 4 to 8 °C. If samples cannot be centrifuged immediately store them in an ice bath (up to 60 min) until centrifugation. Two plasma aliquots will be obtained and stored in polypropylene tubes. The first aliquot should contain at least 1.5 mL plasma whereas the second aliquot should contain the remaining plasma. Within a maximum time of 1 hour after sampling at room temperature, the samples should be stored in a freezer. Until shipment on dry ice to the analytical laboratory, plasma samples will be stored frozen in an upright position at about –20°C or below. The second aliquot will be shipped after the bioanalyst has acknowledged safe arrival of the first aliquot. At the analytical laboratory the plasma samples will be stored at about –20°C or below until analysis

At a minimum, the sample tube labels should list the following information: BI trial number, subject number, visit, and planned sampling time. Further information such as matrix and analyte may also be provided.

After completion of the trial the plasma samples may be used for further methodological investigations, e.g. for stability testing, assessment of metabolites. However, only data related to the analyte and/or its metabolite(s) including anti-drug antibodies (if applicable) will be generated by these additional investigations. The study samples will be discarded after completion of the additional investigations but not later than 5 years upon the final study report has been signed.

### **5.5.3 Analytical determinations**

#### **5.5.3.1 Analytical determination of analyte plasma concentration**

Boehringer Ingelheim Pharma GmbH & Co. KG  
Drug Metabolism and Pharmacokinetics Germany, G144  
[name]

Boehringer Ingelheim Pharma GmbH & Co. KG  
Drug Metabolism and Pharmacokinetics Germany, G144  
[name]

Analysis of ethinylestradiol and levonorgestrel in plasma study samples will be performed using validated liquid chromatography tandem mass spectrometry assays (LC-MS/MS) in the laboratory:

## **6. INVESTIGATIONAL PLAN**

### **6.1 VISIT SCHEDULE**

Exact times of measurements outside the permitted time windows will be documented. The acceptable time windows for screening and end of trial examination are given in the Flow Chart.

Study measurements and assessments scheduled to occur 'before' trial medication administration on Days 17, 18 and 29 are to be performed and completed within a 2 h-period prior to the trial drug administration.

The acceptable deviation from the scheduled time for vital signs, ECG and laboratory tests will be  $\pm$  60 min.

For PK sampling, pre-dose PK samples (nominal time, 0 hours) on Days 17, 18 and 29 have to be performed within 10 minutes before each morning administration.

Acceptable deviations will be  $\pm$  5 minutes for collection of samples within 1 hour after drug administration in the morning,  $\pm$  10 minutes for collection of samples within up to 12 hours after drug administration in the morning, and  $\pm$  30 minutes for collection of samples within up to 24 hours after drug administration in the morning and  $\pm$  60 minutes samples collected after 24 hours after drug administration in the morning. Blood sampling for plasma trough concentration is to be performed within 10 minutes before each morning administration.

If scheduled in the Flow Chart at the same time as a meal, blood sampling, vital signs and 12-lead ECG recordings have to be done first. Furthermore, if several measurements including venipuncture are scheduled for the same time, venipuncture should be the last of the measurements due to its inconvenience to the subject and possible influence on physiological parameters.

For planned individual plasma concentration sampling times refer to the [Flow Chart](#). While these nominal times should be adhered to as closely as possible, the actual sampling times will be recorded and used for determination of pharmacokinetic parameter.

If a subject misses an appointment, it will be rescheduled if possible. The relevance of measurements outside the permitted time windows will be assessed no later than at the Report Planning Meeting.

### **6.2 DETAILS OF TRIAL PROCEDURES AT SELECTED VISITS**

#### **6.2.1 Screening and run-in period**

After having been informed about the trial, all subjects will give their written informed consent in accordance with GCP and local legislation prior to enrolment in the study.

For information regarding laboratory tests (including drug and virus screening), ECG, vital signs, physical examination gynaecological examination including Pap smear, refer to [Sections 5.2.3](#) to [5.2.5](#).

Pharmacogenomic genotyping will be performed in those subjects whose genotypes are not known (for details see [Section 5.3](#)).

Proprietary confidential information © 2017 Boehringer Ingelheim International GmbH or one or more of its affiliated companies

After passing the screening examination the subjects will be allocated to a subject number and will be given a 2-month package of Microgynon® tablets for the run-in-period. The intake of these tablets starts depending on the subjects' actual menstruation cycle and at least 28 days before Day 1 of the treatment period (see [Section 3.1](#)). In the last 7 days of the run-in period, no Microgynon® tablets will be taken to induce a withdrawal bleeding.

### **6.2.2 Treatment periods**

Each subject is expected to participate in the treatment periods (Days 1 to 32).

On Days 16 and 28 study participants will be admitted to the trial site and kept under close medical surveillance for at least 12 h following drug administration. The subjects will then be allowed to leave the trial site after formal assessment and confirmation of their fitness. On all other study days, the study will be performed in an ambulatory fashion.

For details on time points and procedures for collection of plasma samples for PK analysis, refer to [Flow Chart](#) and [Section 5.5.2](#).

The safety measurements performed during the treatment period are specified in [Section 5.2](#) of this protocol and in the Flow Chart. For details on time points for all other trial procedures, refer to the Flow Chart. AEs and concomitant therapy will be assessed continuously from screening until the end of trial examination.

### **6.2.3 End of trial period**

For AE assessment, laboratory tests, recording of ECG and vital signs and physical examination during the end of trial period, see [Sections 5.2.2](#) to [5.2.5](#).

Subjects who discontinue treatment before the end of the planned treatment period should undergo the end of trial visit.

All abnormal values (including laboratory parameters) that are judged clinically relevant by the investigator will be monitored using the appropriate tests until a return to a medically acceptable level is achieved. Adverse events persisting after trial completion must be monitored until they have normalised or have been sufficiently characterised. The end of the trial as a whole is defined by the 'last regular visit completed by last subject' or 'end date of the last open AE' or 'date of the last follow-up test' or 'date of an AE has been decided as sufficiently followed-up', whichever is latest.

## **7. STATISTICAL METHODS AND DETERMINATION OF SAMPLE SIZE**

### **7.1 STATISTICAL DESIGN – MODEL**

#### **7.1.1 Objectives**

The primary objective of this trial is to investigate whether and to what extend BI 409306 affects multiple dose pharmacokinetics of Microgynon® and whether and to what extend Microgynon® affects single dose pharmacokinetics of BI 409306. The trial is designed to allow intra-subject comparisons and will be evaluated statistically by use of an appropriate linear model.

The secondary objective is the evaluation and comparison of several pharmacokinetic parameters between the treatments. The secondary objectives will be assessed by descriptive statistics.

The assessment of safety and tolerability will be an additional objective of this trial, and will be evaluated by descriptive statistics.

#### **7.1.2 Endpoints**

Relative bioavailability is to be determined on the basis of the primary and secondary pharmacokinetic endpoints (see [Section 5.5.1](#)).

Safety and tolerability will be determined on the basis of the parameters specified in [Section 5.2.1](#).

#### **7.1.3 Model**

The statistical model used for the analysis of primary and secondary endpoints will be an ANOVA (analysis of variance) model on the logarithmic scale. This model will include effects accounting for the following sources of variation: 'subjects' and 'treatment'. The effect 'subjects' will be considered as a random effect, whereas the treatment effects will be considered as a fixed effect. The model is described by the following equation:

$$y_{km} = \mu + s_m + \tau_k + e_{km}, \text{ where}$$

$y_{km}$  = logarithm of response (endpoint, see Section 7.1.3) measured on subject m receiving treatment k,

$\mu$  = the overall mean,

$s_m$  = the effect associated with the mth subject, m = 1, 2, ..., n

$\tau_k$  = the kth treatment effect, k = 1, 2,

$e_{km}$  = the random error associated with the mth subject who received treatment k.

## 7.2 NULL AND ALTERNATIVE HYPOTHESES

The relative bioavailability of combined treatment of BI 409306 and Microgynon® compared to multiple treatment of Microgynon® and to single treatment of BI 409306 will be estimated by the ratios of the geometric means (test/reference) for the primary and secondary PK endpoints. Additionally, their two-sided 90% confidence intervals (CIs) will be provided. This method corresponds to the two one-sided t-tests procedure, each at the 5% significance level. Since the main focus is on estimation and not testing, an acceptance range was not specified, that is, no hypothesis will be tested.

Confidence intervals will be computed, but have to be interpreted in the perspective of the exploratory character of the study, i.e. confidence intervals are considered as interval estimates for effects.

## 7.3 PLANNED ANALYSES

### 7.3.1 Primary analyses

The primary and secondary pharmacokinetic endpoints listed in [Section 5.5.1](#) will be calculated according to the BI Standard Operating Procedure (SOP) ‘Standards and processes for analyses performed within Clinical Pharmacokinetics/Pharmacodynamics’ ([001-MCS-36-472](#)).

Primary and secondary pharmacokinetic parameters of a subject will be included in the statistical pharmacokinetic (PK) analyses if they are not flagged for exclusion due to a protocol violation relevant to the evaluation of PK (to be decided no later than in the Report Planning Meeting) or due to PK non-evaluability (as revealed during data analysis, based on the criteria specified below). Exclusion of a subject’s data will be documented in the CTR.

Relevant protocol violations may be

- Incorrect trial medication taken, i.e. the subject received at least one dose of trial medication the subject was not assigned to
- Incorrect dose of trial medication taken
- Use of restricted medications.

Plasma concentrations and/or parameters of a subject will be considered as non-evaluable, if for example

- the subject experienced emesis that occurred at or before two times median  $t_{max}$  of the respective treatment (Median  $t_{max}$  is to be determined excluding the subjects experiencing emesis),
- a pre-dose concentration is >5% of the  $C_{max}$  value of that subject
- missing samples/concentration data at important phases of PK disposition curve.

Proprietary confidential information © 2017 Boehringer Ingelheim International GmbH or one or more of its affiliated companies

The PK parameter analysis set (PKS) includes all subjects in the Treated Set (TS) who provide at least one primary or secondary PK parameter that was not excluded according to the description above. Thus, a subject will be included in the PKS, even if he/she contributes only one PK parameter value for one period to the statistical assessment.

Subjects who are not included in the PKS (refer to [Section 7.3.1.](#)) will be reported with their individual plasma concentrations and individual pharmacokinetic parameters; however, they will not be included in descriptive statistics for plasma concentrations, pharmacokinetic parameters or other statistical assessment.

Concentrations will be used for graphs and calculations in the format that is reported in the bioanalytical report. Only concentrations within the validated concentration range and actual sampling times will be used for the calculation of PK parameters. Concentrations used in the pharmacokinetic calculations will be in the same format provided in the bioanalytical report, (that is, to the same number of decimal places provided in the bioanalytical report).

Plasma concentrations will be plotted graphically versus time for all subjects as listed in the drug plasma concentration-time tables. For the presentation of the mean profiles, the arithmetic mean, geometric mean and the planned blood sampling times will be used.

If a predose concentration value is greater than 5% of  $C_{max}$ , the subject's pharmacokinetic data will be not included in any statistical evaluations, in accordance with international guidances. The individual pharmacokinetic parameters of such a subject will be calculated and listed separately. If a predose concentration is above BLQ, but less than or equal to 5% of the subject's  $C_{max}$  value, the subject's data without any adjustments will be included in all pharmacokinetic measurements and calculations.

Point estimates of bioavailability, the intra-subject ratios of the geometric means (test/reference) for the primary and secondary endpoints (see [5.5.1.1](#), [5.5.1.2](#)), and their two-sided 90% confidence intervals (CIs) will be provided.

To this end, the PK endpoints will be log-transformed (natural logarithm) prior to fitting the ANOVA model (cf. [Section 7.1.3](#)). For each endpoint, the difference between the expected means for  $\log(T)-\log(R)$  will be estimated by the difference in the corresponding adjusted means (Least Squares Means), and a two-sided 90% confidence interval based on the t-distribution will be computed. These quantities will then be back-transformed to the original scale to provide the point estimate and 90% CIs for each endpoint.

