4. CHANGES IN THE PLANNED ANALYSIS OF THE STUDY

There will be no changes in the planned analysis of the study.

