The data format for descriptive statistics of concentrations will be identical with the data format of the respective concentrations. The descriptive statistics of PK parameters will be calculated using the individual values with the number of decimal places as provided by the evaluation program. Then the individual values as well as the descriptive statistics will be reported with three significant digits in the CTR.

Tabulations of frequencies for categorical data will include all possible categories and will display the number of observations in a category, as well as the percentage (%) for each treatment group. Percentages will be rounded to one decimal place and will be based on all subjects in the respective subject set whether they have non-missing values or not. The category 'missing' will be displayed only if there are actually missing values.

Units of variables should be given in the titles or column/row descriptors in square brackets (e.g. [mg]).

Exclusion of PK parameters

The ADS ADPP contains column variables APEXC and APEXCO indicating inclusion/exclusion (APEXC) of a PK parameter and an analysis flag comment (APEXCO). All analyses based on the PKS will include parameters if they are not flagged for exclusion; that is APEXC is equal to "Included".

Exclusion of PK concentrations

The ADS ADPC (PK concentrations per time-point or per time-interval) contains column variables ACEXC or ACEXCO indicating inclusion/exclusion (ACEXC) of a concentration and an analysis flag comment (ACEXCO). Exclusion of a concentration depends on the analysis flag comment ACEXCO. For example, if ACEXCO is set to 'ALL CALC', the value will be excluded for all types of analyses based on concentrations. If ACEXCO is set to 'DESC STATS' the value will be excluded from descriptive evaluations per planned time point/time interval. If ACEXCO contains the addition 'TIME VIOLATION' or 'TIME DEVIATION' the value can be used for further analyses based on actual times. If ACEXCO is set to 'HALF LIFE' the value will be excluded from half-life calculation only; the value is included for all other analyses.

Further details are given in 001-MCS-36-472_RD-01 "Noncompartmental Pharmacokinetic / Pharmacodynamic Analyses of Clinical Studies" (4) and 001-MCS-36-472_RD-03 "Description of Analytical Transfer Files and PK/PD Data Files" [\(7\)](#).

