7.4 PRIMARY ENDPOINT(S)

The analysis will be performed as defined in the CTP, Sections 7.3.1-2.

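### The 5% pre-dose exclusion is not limited to BI 409306; applied as written to steady-state troughs, it removes essentially all levonorgestrel data from the part 2 primary analysis

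*Protocol*

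**What the plan says.** Protocol section 7.3.1 gives the criterion twice. The first is in a list of examples: "Plasma concentrations and/or parameters of a subject will be considered as non-evaluable" when, among other things, "a pre-dose concentration is >5% of the" subject's Cmax. The second comes later in the section as a flat instruction: above 5% of Cmax, the subject's "pharmacokinetic data will be not included in any statistical evaluations, in accordance with international guidances". Individual parameters are still calculated and listed separately. Neither statement names an analyte, a dosing regimen or a part of the trial. The section as a whole governs all primary and secondary PK parameters.

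The same section commits to "Point estimates of bioavailability, the intra-subject ratios of the geometric means (test/reference) for the primary and secondary endpoints", with 90% confidence intervals. Under Protocol section 5.5.1.1, the primary endpoints include AUC0-24,ss and Cmax,ss of both EE and LNG.

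The SAP leaves this as it is. Section 6.3 repeats the criterion, section 7.4 states "The analysis will be performed as defined in the CTP, Sections 7.3.1-2", and section 4 states "There will be no changes in the planned analysis of the study".

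Protocol section 6.1 requires "pre-dose PK samples (nominal time, 0 hours) on Days 17, 18 and 29" and also refers to trough sampling before each morning dose. Only Microgynon is given on Day 17, so the protocol's term for a pre-dose sample covers EE and LNG. Protocol section 3.2 says the Microgynon dosing period was chosen to reach steady state.

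**The concern.** A limit on the pre-dose concentration detects carry-over when the subject should be drug-free before the dose. That is the position for the single doses of BI 409306 on Days 18 and 29. It is not the position for EE and LNG on Days 17 and 18, where a sizeable pre-dose level is what the design sets out to achieve.

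There are six primary comparisons: AUC and Cmax for each of BI 409306, EE and LNG. If the LNG trough normally exceeds 5% of Cmax, the exclusion and the promised estimates cannot both be carried out for the two LNG comparisons. The analyst would have to set aside a written, mandatory exclusion for a primary endpoint under a SAP that declares no departure from the protocol.

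For EE the rule could apply to some subjects and not others. Those kept would be the ones with the lowest trough-to-peak ratios, a subset selected on the pharmacokinetics being measured.

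**Working it through.** The documents give no trough/Cmax ratio and no expected number of exclusions, so there is no planned figure to reproduce. The check asks how the expected trough compares with 5% of Cmax.

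**Inputs from the protocol**
- Dosing interval 24 h (section 3.1, once daily from Day 1).
- LNG: terminal half-life about 25 h, tmax 1 to 2 h (section 1.2.2).
- EE: terminal half-life 10 to 20 h, tmax 1 h (section 1.2.2).
- 16 subjects (section 7.6).
- Day 17 dose at 384 h after the Day 1 dose (Flow Chart). 384/25 = 15.4 LNG half-lives, so treating LNG as at steady state is sound.

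**Step 1: simple decay from the peak.** Ratio = 2^(−(24 − tmax)/t½).
- LNG, tmax 1 h: 2^(−23/25) = 0.529. LNG, tmax 2 h: 2^(−22/25) = 0.543. Dividing by 0.05 gives 10.6 and 10.9 times the cut-off.
- EE, tmax 1 h: 2^(−23/10) = 0.203; 2^(−23/15) = 0.345; 2^(−23/20) = 0.451.

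A steady-state one-compartment model with first-order absorption, with ka solved to match tmax, gives nearly the same: LNG 0.532 and 0.552; EE 0.207, 0.349 and 0.454. For the LNG ratio to fall to 5% by simple decay, the half-life would have to be ln2 × (24 − tmax)/ln20, which is 5.3 h (tmax 1 h) or 5.1 h (tmax 2 h), against the stated 25 h.

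**Step 2: allow for a distribution phase.** This lowers the trough relative to the peak. Let f be the share of the single-dose peak that belongs to the terminal phase, with the fast phase gone by 24 h. With r = 2^(−24/t½) and a = r/(1 − r), the ratio is R = f·a/(1 + f·a). The documents do not give f, so it is an assumption and a range is shown.

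For LNG, r = 0.514 and a = 1.058. For EE, a = 0.234, 0.492 and 0.771 at half-lives of 10, 15 and 20 h. Setting R = 0.05 gives the break-even f = (0.05/0.95)/a: 0.050 for LNG, and 0.225, 0.107 and 0.068 for EE.

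**Step 3: expected number passing.** Assume R varies log-normally between subjects around the value shown, with a CV of 30% or 50% (also assumptions). The expected number at or below 5% is 16 × Φ[(ln 0.05 − ln R)/s], with s = √ln(1 + CV²), i.e. 0.294 or 0.472.

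| Analyte, t½ | f | R | Passing of 16 (CV 30% / 50%) |
|---|---|---|---|
| LNG, 25 h | 0.3 | 0.241 | <0.01 / <0.01 |
| LNG, 25 h | 0.2 | 0.175 | <0.01 / 0.06 |
| LNG, 25 h | 0.1 | 0.096 | 0.2 / 1.4 |
| LNG, 25 h | 0.05 | 0.050 | 7.9 / 7.9 |
| EE, 10 h | 0.3 | 0.066 | 2.9 / 4.5 |
| EE, 10 h | 0.2 | 0.045 | 10.4 / 9.5 |
| EE, 10 h | 0.1 | 0.023 | 15.9 / 15.2 |
| EE, 15 h | 0.2 | 0.090 | 0.4 / 1.7 |
| EE, 15 h | 0.1 | 0.047 | 9.4 / 8.9 |
| EE, 20 h | 0.1 | 0.072 | 1.8 / 3.6 |

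Under the one-compartment ratios of step 1, fewer than 0.1 of 16 pass for EE at any of the three half-lives, and practically none for LNG.

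**The case against.** The best defence is that the rule was meant only for BI 409306. The protocol writes Cmax for BI 409306 and Cmax,ss for EE and LNG, and the rule says Cmax. Its companion sentence, which allows a quantifiable pre-dose value up to 5% to be used unadjusted, treats such a value as unusual, which fits single dosing only. The sponsor's PK procedure (001-MCS-36-472), which governs the endpoint calculations, was not available and may limit the rule. The trial is exploratory, parameters are listed regardless, and exceptional cases go to the Report Planning Meeting.

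The reading of intent is probably right, and the SOP point cannot be ruled out. Neither cures the text. The protocol's abbreviation list defines Cmax for any analyte, and section 5.5.1.1 describes Cmax and Cmax,ss in the same words, so the notation creates no exemption. The exclusion is written out in full in the protocol without reference to the SOP. Although the first statement is only an example, the second is mandatory. Deciding the scope at the Report Planning Meeting would mean interpreting an exclusion for a primary endpoint late, in an open-label trial.

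It is also fair that f and the CVs are not in the documents. The LNG conclusion weakens as f approaches 0.05, where about half the profiles would pass. The EE range is too wide to say more than that the loss is uncertain.

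**Conclusion.** The concern holds. As written, the 5% rule covers steady-state EE and LNG, and no visible text exempts them. From the protocol's own half-life and tmax, the LNG trough is about 53–54% of Cmax under simple decay. It stays above 5% unless the terminal phase makes up only about one twentieth of the single-dose peak. The two LNG primary endpoints would therefore lose essentially all 16 subjects for f above about 0.1; at f = 0.1 itself, 0.2 to 1.4 would be expected to remain. For EE the loss runs from almost none to all, depending on half-life and f.

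No data would be destroyed, because the parameters are still listed. The fault is that the written plan rules out estimates it also promises. The LNG conclusion rests on the stated half-life and tmax and on the assumed range of f. The expected counts rest also on the assumed CVs of 30% and 50%.

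There is a lesser inconsistency of level. The mandatory sentence removes the subject's PK data as a whole, whereas SAP section 7 works by parameter: "All analyses based on the PKS will include parameters if they are not flagged for exclusion". This needs tidying, but it is not evidence that part 1 data would be lost.

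**What to change.** In Protocol section 7.3.1 and SAP section 6.3:

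1. Limit the 5% pre-dose criterion to BI 409306, and apply it only to the affected profile (T1 on Day 18 or R1 on Day 29).
2. State that it does not apply to EE and LNG at steady state on Days 17 and 18.
3. Replace the exclusion of the subject's PK data with exclusion of the affected parameters, so that both statements in Protocol section 7.3.1 and SAP section 6.3 agree with the parameter-level flag in SAP section 7.
4. Record the clarification in SAP section 4, which at present declares no changes.

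With the rule limited in this way, it removes no EE or LNG data, and all 16 subjects stay eligible for part 2 on this criterion. The cost is one or two sentences in each document, with no extra samples or subjects. If the sponsor's PK procedure already contains this limit, the change only copies it into the plan.
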